## On study monitoring of liver function test (LFT) for all patients

LFTs should be monitored for all patients as per protocol, or more frequently if clinically indicated.

At any time during the study, if  $ALT > 5 \times ULN$  in patients with baseline  $ALT \le 3 \times ULN$ , or if  $ALT > 8 \times ULN$  in patients with baseline  $ALT > 3 \times ULN$  but  $\le 5 \times ULN$ : immediately

- 1. Perform test(s) for viral hepatitis infection or reactivation: all patients should be screened with viral hepatitis panel (HAV-Ab-IgM, HBsAg, HBcAb-IgM, and HCV-Ab). In addition:
  - a. Patients who have HBV-DNA monitoring during the study should be re-tested for HBV-DNA immediately; refer to Table 6-6 for definition and management of HBV reactivation.
  - b. Patients who have HCV-RNA monitoring during the study should be re-tested for HCV-RNA immediately; refer to Table 6-7 for definition and management of HCV reactivation.
- 2. If any of the above tests indicate:
  - a. HBV reactivation: refer to Table 6-6 for management guidelines.
  - b. HCV reactivation: refer to Table 6-7 for management guidelines.
  - c. New viral infection: immediately interrupt EGF816 and gefitinib dosing, consult a physician with expertise in managing viral hepatitis and contact study PI for further discussion.
- 3. Perform other relevant tests/procedures as clinically indicated.
- 4. Follow the dosing modification for ALT elevation according to guidelines in Table 6-4.

## 6.1.4 Management of diarrhea

## Table 6-8: Guidelines for management of diarrhea

Diarrhea a	
Grade 1	Maintain dose level but adjust anti-diarrheal treatment
Grade 2 (despite maximal antidiarrheal medication)	Omit gefitinib and EGF816 until resolved to $\leq$ Grade 1, then reintroduce EGF816 same dose level; if diarrhea remains $\leq$ grade 1 after at least a week on EGF816, resume gefitinib. If diarrhea returns as $\geq$ Grade 2, then omit both drugs until resolved to $\leq$ Grade 1, then decrease both drugs by one dose level and reintroduce one at a time as above.
Grade 3 (despite maximal antidiarrheal medication)	Omit both drugs until resolved to $\leq$ Grade 1, then decrease EGF816 and gefitinib by 1 dose level and reintroduce one at a time (as above) if diarrhea is grade $\leq$ 1 after at least one week on EGF816.
Grade 4 (despite maximal antidiarrheal medication)	Omit both drugs until resolved to $\leq$ Grade 1, then decrease EGF816 and gefitinib by 1 dose level and reintroduce one at a

	time (as above) if diarrhea is grade $\leq 1$ after at least one week on EGF816.
--	--

a. Antidiarrheal medication is recommended at the first sign of abdominal cramping, loose stools or overt diarrhea.

Grade 1-2 diarrhea should be managed with Loperamide (4mg at first onset, followed by 2mg every 2-4 hours until diarrhea free for 12 hours with maximum daily dose of 16 mg per 24 hours.) If loperamide is ineffective, consider adding Lomotil (5 mg, four times a day), or tincture of opium (15-20 drops orally every 4 hours) or octreotide (150 to 300 mcg SQ twice daily).

6.1.5 Management of rash

Both EGF816 and gefitinib are known to cause rash, but the rash typically associated with each drug is distinct. Gefitinib-associated rash is generally an acneiform, papular rash while that associated with EGF816 is more commonly maculopapular, pruritic and without true acneiform lesions. The management of each type of rash is different, and both are outlined below.

Type of care	Action			
Prevention/Prophylaxis	Avoid unnecessary exposure to sunlight			
Starting from Day 1 for all patients	Apply broad-spectrum sunscreen with SPF≥15 at least twice daily			
	Use thick, alcohol-free emollient cream (e.g. glycerin and cetomacrogol cream) on dry areas of the body at least twice daily			
Symptomatic lesions	Pruritic lesions: cool compresses and oral antihistamine therapies			
	Desquamation: thick, alcohol-free emollient cream and mild soap			
	Paronychia: antiseptic bath and topical antibiotics; if no improvement,			
	consult dermatologist Infected lesions: appropriate topical or systemic antibiotics			
Patients who develop rash/skin toxicities should be evaluated by a qualified physician and				
receive symptomatic and supportive care management.				

Table 6-9: Guidelines for prevention and symptomatic care of rash/skin toxicities

#### Table 6-10. Guidelines for management of maculopapular rash

CTCAE Grade	Adverse Event Management	Action and Dose
		Modification
Grade 1	Initiate appropriate	Continue both study drugs at
	symptomatic care (Refer to	same dose level
	Table 6-9)	
	Use mild-strength topical	
	steroid (e.g. 1%	
	hydrocortisone cream) on	

	affected areas			
Grade 2	Re-assess after 1 week         Initiate appropriate	Continue both study drugs at		
	symptomatic care (Refer to Table 6-9) Use moderate-strength topical steroid (e.g. 2.5% hydrocortisone cream or 0.5% fluticasone cream) on affected areas PLUS low-dose oral steroid (e.g. 5mg-10mg PO QD for 1 week) with taper	same dose level If no recovery or worsened within 1 week, interrupt EGF816 and gefitinib until recovery to $\leq$ Grade 1. Once rash has recovered to $\leq$ Grade 1, restart EGF816 at one level reduced from the previous dose level  . Drugs should be		
	Re-assess after 1 week	reintroduced one at a time; if no recurrent rash occurs with introduction of EGF816, gefitinib can be resumed at the original dose level.		
Grade ≥ 3	Initiate appropriate symptomatic care (Refer to Table 6-9) Use moderate-strength topical steroid on affected areas PLUS mid-dose oral steroid (e.g. 20- 40mg PO QD for 1 week) with taper over 1-2 weeks or IV steroid (e.g. methylprednisolone 20-30mg IV BID for 3 days) if clinically indicated Consult dermatologist	Interrupt both study drugs until rash recovers to $\leq$ Grade 1. Once recovers to $\leq$ Grade 1, restart EGF816 at one level reduced from the previous dose level. Drugs should be reintroduced one at a time; EGF816 should be resumed first and, if no recurrent rash occurs within a week, gefitinib can be resumed at original dose level. Oral antihistamine therapies (e.g. levocetirizine 5mg QD, desloratadine 5mg QD, or fexofenadine 180 mg QD) should be given concurrently with study drugs for 4 weeks when restarting treatment. If no recovery to $\leq$ Grade 2 within 3 weeks, permanently discontinue EGF816. Gefitinib can be continued. Patients who develop more		
		than 1 episode of Grade $\geq 3$ rash will be permanently discontinued from EGF816.		
1. Maculopapular rash ir	ncludes macular rash, papular ras			

2. For all grades of maculopapular rash, consider skin biopsy for pathologic evaluation.

# Table 6-11. Guidelines for management and dose modification of other rashes including acneiform rash.

	Adverse Event	Adverse Event		
	Management	Management		
Grade 1	Monitor for change in severity and consider symptomatic and/or topical treatment (Refer to Table 6- 9) Re-assess after 2 weeks	Continue study drug at same dose level		
Grade 2	Initiate appropriate symptomatic care (Refer to Table 6-9) Depending on the type of rash, a variety of agents can be used including mild to moderate strength steroid creams, topical or systemic antibiotics, topical or systemic antihistamines, and retinoid creams. Re-assess after 2 weeks	Continue study drugs at same dose level If no recovery or worsened within 2 weeks, interrupt both study drugs until rash recovers to $\leq$ Grade 1 Once rash recovers to $\leq$ Grade 1, then restart gefitinib at one reduced dose level and continue same EGF816 dose.		
Grade 3	Initiate appropriate symptomatic care (Refer to Table 6-9) Depending on the type of rash, a variety of agents can be used including mild to moderate strength steroid creams, low-dose oral steroids, topical or systemic antibiotics, topical or systemic antihistamines, and retinoid creams. Consult dermatologist	Interrupt both study drugs until rash recovers to $\leq$ Grade 1. Once rash recovers to $\leq$ Grade 2, restart gefitinib at one reduced dose level. If no rash $\geq$ grade 1 recurs after at least 7 days on gefitinib, EGF816 can be then be resumed at the original dose level. If rash $\geq$ grade 1 recurs within 1 week, interrupt both drugs again until rash recovers to $\leq$ Grade 1, then resume gefitinib at the reduced dose level, monitor for recurrence and then resume EGF816 reduced by one dose level.		

If no recovery to $\leq$ Grade 2
within 3 weeks, permanently
discontinue study drugs.
Patients who develop more
than 1 episode of Grade $\geq 3$
rash will be permanently
discontinued from study
treatment

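### Table 6-11, Grade 3 row: both drugs are held until rash is Grade 1 or lower, yet gefitinib restarts at Grade 2 or lower, and nothing says which governs

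*Combined protocol and SAP*

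**What the plan says.** Table 6-11 (Section 6.1.5) covers rashes other than maculopapular rash, including acneiform rash. The action cell of its Grade 3 row contains these rules:

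- Hold, then restart: "Interrupt both study drugs until rash recovers to $\leq$ Grade 1. Once rash recovers to $\leq$ Grade 2". The second of these sentences ends: "Grade 2, restart gefitinib at one reduced dose level".
- EGF816: if no rash at or above "grade 1 recurs after at least 7 days on gefitinib, EGF816 can be then be resumed at the original dose level".
- Recurrence within one week: both drugs are stopped again until rash is at or below "Grade 1, then resume gefitinib at the reduced dose level, monitor for recurrence and then resume EGF816 reduced by one dose level".
- Discontinuation: "If no recovery to $\leq$ Grade 2" within three weeks, both drugs stop permanently.

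The Grade 2 row of the same table covers rash that has not improved or has worsened within two weeks. It tells sites to "interrupt both study drugs until rash recovers to" Grade 1 or lower, and continues: "Once rash recovers to $\leq$ Grade 1, then restart gefitinib at one reduced dose level". For maculopapular rash of Grade 3 or higher, Table 6-10 also holds both drugs until Grade 1 or lower, and then says: "Once recovers to $\leq$ Grade 1, restart EGF816 at one level reduced from the previous dose level".

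**The concern.** Gefitinib is one of the two drugs that the first sentence holds, so the first two sentences set different conditions for the same act. Two investigators who each follow the table could treat the same Grade 2 rash differently: one keeps gefitinib on hold, the other restarts it.

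This affects exposure to treatment while a toxicity is unresolved, and the time patients spend off one or both drugs. Safety and tolerability are a secondary objective (Section 1.3), and Section 5.1 refers to participating sites in the plural.

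The difference can also go beyond timing. Section 6 requires discontinuation when a toxicity-related interruption exceeds 28 days. A rash that falls to Grade 2 within three weeks and stays there escapes the three-week rule in the cell. Under the first sentence the hold continues and can run past 28 days. Under the second, gefitinib has already restarted. The same patient could leave treatment or stay on it, subject to the case-by-case exceptions that Section 6 allows.

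**Working it through.** No arithmetic applies. The check compares the sentences of the cell with each other and then with the neighbouring rules.

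**Step 1. Apply the first two sentences to each possible state after a Grade 3 rash.**

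| Current rash grade | First sentence (hold until ≤ 1) | Second sentence (restart gefitinib at ≤ 2) | Result |
|---|---|---|---|
| 3 | hold | no restart | agree |
| 2 | hold | restart gefitinib | conflict |
| 1 or none | hold ends | restart gefitinib | agree |

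The conflict is confined to the interval in which rash is Grade 2.

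**Step 2. Look for a reading that removes the conflict.**

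- Grade 2 for gefitinib and Grade 1 for EGF816: this fails, because the first sentence names both drugs and EGF816 has its own condition tied to at least 7 days on gefitinib.
- The three-week rule: it uses Grade 2, but for permanent discontinuation, which is a different action.
- Section 5.2.2: before each cycle, toxicity that required a delay must have resolved to Grade 1 or pre-therapy baseline. This bears on cycle starts; it does not mention Table 6-11 and does not settle a mid-cycle restart.
- Section 6.1: investigators may depart from the guidelines in individual cases. This does not say which grade is the default.

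**Step 3. Compare with the neighbouring rules.**

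| Rule | Hold until | Restart at |
|---|---|---|
| Table 6-11, Grade 3, first hold | ≤ 1 | ≤ 2 |
| Table 6-11, Grade 3, second hold | ≤ 1 | after that recovery |
| Table 6-11, Grade 2 | ≤ 1 | ≤ 1 |
| Table 6-10, Grade ≥ 3 | ≤ 1 | ≤ 1 |
| General Grade 3 rule, Section 6.1 | ≤ 1 | ≤ 1 |

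Only the first hold in the Grade 3 row of Table 6-11 has unequal grades. No text explains the difference.

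**Step 4. Follow the sequence to EGF816.** Resumption requires that no rash of Grade 1 or higher *recurs* after at least 7 days on gefitinib, and recurrence within a week stops both drugs again.

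- Restarted with no rash: the criterion is clear.
- Restarted with Grade 1 rash, which both sentences permit: rash of Grade 1 is already present. A site may call it persistence and proceed, or recurrence and stop.
- Restarted with Grade 2 rash, which only the second sentence permits: the same ambiguity, with more residual rash.

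The ambiguity at Grade 1 exists under either threshold. The conflict in Step 1 extends it to Grade 2.

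**The case against.** The strongest case on the other side is that the practical divergence is narrow. It exists only while rash is Grade 2, Section 5.2.2 limits it at cycle starts, and the guidelines are recommendations open to clinical judgment, with further exceptions after discussion with the principal investigator. The number of sites is not stated. Section 5.1 excludes rash from the run-in toxicity definition, so the cell should not alter that decision. All of this stands and limits the reach of the point. It does not say which grade a site should start from.

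It is also fair to say that *recurs* can be read as re-emergence or worsening after restart. The EGF816 criterion is therefore ambiguous; a claim that it cannot be applied would go too far. Staged thresholds can also be legitimate, as the separate three-week rule shows, so the documents do not establish that one recovery grade must run through the whole cell.

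A reader might estimate the patients affected from the Grade 3 or 4 rash rate in Section 2.2.2: 0.155 × 36 = 5.6, or about five or six patients. The documents do not support that use. The 15.5% is a grouped rash term for EGF816 alone, pooled over seven dose levels from 75 to 350 mg. Section 6.1.5 describes EGF816 rash as more commonly maculopapular, which falls under Table 6-10, where the grades agree. The figure also includes Grade 4, for which Table 6-11 has no row.

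A reader might also infer from the neighbouring rules that Grade 1 was intended. They show that the mismatch is local to this cell. They do not show what the sponsor meant.

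**Conclusion.** The point holds as an internal contradiction in a dosing rule. Two consecutive sentences in the Grade 3 row of Table 6-11 give opposite instructions on gefitinib for a patient whose rash is Grade 2, and the EGF816 step that follows is ambiguous for anyone restarted with residual rash.

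Its size in patients is unknown, because the documents give no Grade 3 rate for the rashes under Table 6-11, whether for gefitinib or for the combination. Sample size, alpha and power are untouched. What is at stake is consistent exposure and safety management between investigators. The conclusion rests only on the printed grades, which are legible in the text and show no sign of redaction.

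**What to change.** The sponsor should reconcile the hold sentence and the gefitinib restart sentence in the Grade 3 row of Table 6-11. The EGF816 resumption and re-interruption criteria should then be made consistent with the result, including what counts as recurrence when rash is still present at restart. Which grade or grades apply is the sponsor's clinical decision. The cost is a correction to one table cell; no change to the design or the analysis follows from it.

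### Table 6-11, Grade 3 rash: both drugs are held until Grade 1 or below, but the next sentence restarts gefitinib at Grade 2 or below, so the rule conflicts at Grade 2

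*Combined protocol and SAP*

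**What the plan says.** Section 6.1.5 manages rash by type: Table 6-10 covers maculopapular rash, and Table 6-11 covers other rashes, including acneiform rash. The Grade 3 row of Table 6-11 gives this sequence:

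- Hold and restart: both drugs are interrupted "until rash recovers to $\leq$ Grade 1. Once rash recovers to $\leq$ Grade 2, restart gefitinib at one reduced dose level".
- Go-ahead for EGF816 at its original dose: "If no rash $\geq$ grade 1 recurs after at least 7 days on gefitinib".
- Re-interruption: "If rash $\geq$ grade 1 recurs within 1 week, interrupt both drugs again until rash recovers to $\leq$ Grade 1". Gefitinib then returns at the reduced level, and the site is to "monitor for recurrence and then resume EGF816 reduced by one dose level".
- Discontinuation: both drugs stop for good if the rash has not come down to Grade 2 or below in 3 weeks, or after a second episode of Grade 3 or higher.

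Neighbouring rules use one grade for both hold and restart. The Grade 2 row of Table 6-11 holds to Grade 1 or below and then says "Once rash recovers to $\leq$ Grade 1, then restart gefitinib at one reduced dose level". The Grade 3-or-higher row of Table 6-10 says "Interrupt both study drugs until rash recovers to $\leq$ Grade 1. Once recovers to $\leq$ Grade 1, restart EGF816". Table 6-3, the general rule, holds both drugs for a Grade 3 toxicity until Grade 1 or below and reintroduces them from there.

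Section 6 discontinues a patient whose toxicity hold exceeds 28 days, and allows at most two dose reductions per drug. Section 6 also permits exceptions after discussion with the principal investigator. Section 6.1 lets the treating investigator modify the guidelines in individual cases.

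**The concern.** Two adjacent sentences set different grades for the same decision. Two investigators who both follow the cell could restart gefitinib at different grades after the same Grade 3 rash, and neither would be departing from the protocol.

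The rule carries some weight. Section 5.1 leaves rash out of the run-in toxicity definition because Grade 3 rash usually responds to a dose hold. The hold rules in Tables 6-10 and 6-11 are therefore the main control on Grade 3 rash and should give one answer.

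The second question is what happens at a Grade 1 recurrence. The re-interruption rule is entered at Grade 1 and released at Grade 1, yet it leads to a lower EGF816 dose. It is unclear whether Grade 1 was meant to enter that branch.

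**Working it through.** The plan states no statistical figure on this point. The check compares the grades (0 to 4) at which each instruction applies, taking the inequality signs as printed.

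**Hold against restart (Table 6-11, Grade 3 row)**
- Hold released at grades {0, 1}.
- Gefitinib restarted at grades {0, 1, 2}.
- Restart minus release = {2}.

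Grade by grade:
- Grades 0 and 1: both sentences allow gefitinib.
- Grade 2: the hold keeps it off and the next sentence restarts it.
- Grades 3 and 4: both keep it off.

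The conflict is at Grade 2 only.

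**The same comparison elsewhere**
- Table 6-3, Grade 3: release {0, 1}, restart {0, 1}, no difference.
- Table 6-10, Grade 3 or higher: release {0, 1}, restart {0, 1}, no difference.
- Table 6-11, Grade 2 row: release {0, 1}, restart {0, 1}, no difference.

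With the restart in the Grade 3 row set to {0, 1}, restart minus release is empty there too.

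**Cost of that edit**

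A rash at Grade 2 by 3 weeks (21 days) escapes the cell's own discontinuation line but stays on hold. If both clocks start with the hold (an assumption, since the cell does not say when the 3 weeks begin), 28 - 21 = 7 days remain before the Section 6 limit requires discontinuation.

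**Re-interruption trigger against its release**
- Trigger {1, 2, 3, 4}; release {0, 1}; shared grade {1}.
- Recurrence at Grade 2: trigger met, release not met, so the hold is real.
- Recurrence at Grade 3 or higher: this is a second such episode, so treatment is discontinued.
- Recurrence at Grade 1 with EGF816 still off: only gefitinib is newly stopped, and its release is already met. EGF816 nevertheless comes back one level lower.
- Recurrence at Grade 1 after EGF816 has resumed: both drugs stop, gefitinib returns first, and EGF816 stays off during monitoring. The hold then has content.

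If the branch is followed, EGF816 falls from 100 to 75 mg, (100 - 75)/100 = 25%, with 2 - 1 = 1 reduction left. From 75 mg it falls to 50 mg, (75 - 50)/75 = 33%, with 2 - 2 = 0 left. The step-down may be deliberate caution after a Grade 3 rash and is not counted here as an error.

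**The case against.** On the hold and restart, the best reply is that these are recommended guidelines which the investigator may modify, so the wording binds nobody. That lessens the practical effect. It does not say which grade is the default, and a discretion clause needs a default to depart from.

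One could also argue that Grade 2 was intended, because the 3-week discontinuation line names Grade 2. But Table 6-10 carries the same 3-week line alongside a hold and restart at Grade 1 or below, so the line does not settle the matter. Nor can the two sentences be read as a staggered restart, with EGF816 waiting for Grade 1 and gefitinib for Grade 2, because the hold sentence covers both drugs.

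On the re-interruption rule, a reader might infer that the second hold is redundant and that the trigger must move above Grade 1. The comparison with diarrhoea in Table 6-8 ("If diarrhea returns as $\geq$ Grade 2, then omit both drugs until resolved to $\leq$ Grade 1") and with Table 6-3, which looks for recurrence above Grade 1, makes this tempting. The documents do not support it, for four reasons:

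- The overlap is at exactly Grade 1; at Grade 2 the hold works.
- Even at Grade 1 the hold is empty only if EGF816 is still off. The sentence follows the one that resumes EGF816 and speaks of stopping both drugs again, so it can equally be read as covering a rash that returns on both drugs.
- The trigger requires that rash *recurs*. Residual Grade 1 or 2 rash at restart is not clearly a recurrence, so it cannot be said that such a patient has already met the trigger.
- Table 6-10, the nearest parallel, also demands no recurrent rash before the second drug returns. A strict standard for rash is therefore not peculiar to this cell.

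These objections stand. They reduce the trigger to a question for the sponsor, and leave the hold and restart conflict untouched.

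**Conclusion.** The Grade 3 row of Table 6-11 contradicts itself for a patient at Grade 2: gefitinib is both held and restarted. This rests on the text as printed and on no numerical assumption. The documents do not say which grade was intended. Grade 1 or below is the likelier default because the hold itself and three neighbouring rules use it.

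Whether a Grade 1 recurrence should start the hold and the EGF816 step-down is unclear and needs the sponsor's answer. Moving that trigger and the matching go-ahead above Grade 1 is a clinical choice.

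The protocol gives no frequency for Grade 3 rash managed under this table, so none is claimed. This is a minor dosing-rule correction. It has no effect on sample size, power or the primary analysis, and no effect on efficacy is claimed.

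**What to change.** In the Grade 3 row of Table 6-11, change the gefitinib restart from Grade 2 or below to Grade 1 or below. This is one threshold in one cell, with no change to visits, data collection or analysis. The 3-week discontinuation line can stay as it is. The cost falls on a patient whose rash stalls at Grade 2: gefitinib stays off longer and, beyond 28 days, Section 6 requires discontinuation unless an exception is agreed. If the sponsor did intend a Grade 2 restart, the hold sentence should be changed to match and the difference from Table 6-10 explained.

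Separately, ask the sponsor to state whether a Grade 1 recurrence triggers the second hold and the EGF816 reduction, and whether the 1-week window runs during gefitinib alone or after EGF816 has resumed. If the sponsor chooses to move the trigger above Grade 1, the go-ahead condition should move with it so that every grade leads to one action. On the reading in which EGF816 is still off, that choice would let EGF816 return at its original dose with Grade 1 rash present soon after a Grade 3 rash, which is more permissive than Table 6-10.
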